## Specific Aim 3:

Conduct a second round of focus groups with Aim 1 existing or former LifeBio users, dementia care professionals, and stakeholders. Conduct a full-scale fidelity trial of the enhanced LifeBio MemoryTM product with staff (n=60) who work within residential care settings (independent, assisted living, and/or nursing home settings) that serve persons living with dementia (n=242).

Focus group participants are reconvened to provide feedback on the revised LifeBio MemoryTM software application. Questions focus around improvements made to the prototype and training materials based on the previous suggestions made by the groups. The full functionality of the application is displayed, and additional recommendations and feedback are elicited. Particular attention is paid to training materials for each group (older adults with dementia and staff), with recommendations and fixes addressed prior to implementation in the fidelity trial. The groups are walked through a hands-on demonstration of their respective user experiences, including the training materials, guided interview process, text-to-speech function, multimedia upload function, and the automated production of life story materials, including the Life Story Book, Snapshot, and Action Plan, using machine learning/Al. Following qualitative, open-ended data collection from the focus group sessions, participants are also asked to complete short user-acceptance testing surveys to validate the design and the overall functionality of the application, as well as the changes based on the recommendations suggested in Aim 1.

Care professionals are trained to implement the revised version of LifeBio Memory™ in their organizations. Staff training is scheduled using a staggered protocol, and tablets preloaded with LifeBio Memory™ are the main medium of self-paced, online

instruction. Each trainee is asked to complete the training within one week of assignment, as well as complete a pre-training, baseline survey that collected demographic information, job history, previous experience with life story work, and attitudes towards person-centered care and older adults with dementia. The app also tracks whether trainees view other support materials from the LifeBio MemoryTM application, namely, the Frequently Asked Questions (FAQs). After training, the staff trainees complete a checklist and a post-training survey on the tablet that gathers their opinion on:

- The length of time spent on training.
- Whether they had difficulty with particular sections/content/materials.
- Whether they feel prepared to conduct life story interviews with older adults with dementia
- Whether they feel comfortable with the basic functionality of LifeBio Memory™
- Whether they feel confident the technology would accurately convey the story of the resident with dementia.
- Whether they have specific questions not covered by the FAQs or the training.
- They also have the opportunity to provide comments on their overall experience via open-ended questions adapted from our previous evaluation questionnaires used in the pilot program.

**Time 1 baseline interviews** are conducted with residents living with dementia and staff members. Separate baseline research interviews (developed from earlier work) are conducted by researcher interviewers with each resident and staff trainee.

Time 1 resident interviews include:

- demographic information
- depression, anxiety, agitation, and loneliness
- perception of whether staff have adequate knowledge of their care preferences and interests
- quality of communication/interactions between the resident and staff
- whether staff have an understanding of the resident's life story
- level of tension and frustration with staff
- general well-being and quality of life.

Interviews with staff are conducted on *each* of their assigned residents (2-6 residents per time wave) and include:

- resident depression, anxiety, agitation, loneliness, and incidence of memory and behavior problems
- their current knowledge of resident care preferences and interests
- utilization of person-centered care practices
- quality of communication between the resident and themselves and other staff
- their current understanding of that resident's life history
- level of tension and frustration with the resident
- perception of the resident's overall well-being and quality of life, as well as their self-efficacy related to providing care.

Life story interviews are completed between trained staff and their assigned residents using the LifeBio MemoryTM tablet app.

After the research interview is completed, a trained staff member conducts a life story interview with a resident within a two-week period. Treatment fidelity is monitored through oversight of the staff administering the life story interviews. LifeBio MemoryTM sessions with residents are audiotaped with the permission of the resident or his/her legal guardian. Trained raters monitor treatment fidelity by rating staff on whether they followed protocols included in their training and used appropriate techniques to elicit life story information from residents. Ratings for each strategy follow a 6-point scale indicating the frequency with which each suggested strategy and/or protocol was used, with scores ranging from 0 (not at all) to 5 (a great deal). Higher scores indicate that the specific strategy was used to a great extent during the interview. Raters begin coding recordings once they reach a threshold reliability greater than an Intraclass Correlation Coefficient (ICC) of .80. Staff participants conducting the resident interviews are prompted to complete a brief electronic survey on the tablet immediately after each of their assigned LifeBio MemoryTM interviews with residents.

The survey questions gather information on satisfaction with:

- interviewing the resident/quality of interaction with the resident
- positive experiences and difficulties encountered using the LifeBio Memory™ tablet app
- perceived advantages of the program
- perception of meeting the program goals
- Staff also have an opportunity to provide feedback in open-ended note fields and will give their perceptions of the importance and usefulness of life story work, whether it is likely to improve resident-staff interactions, and the feasibility and acceptability of the program in their facility.

**Time 2 research interviews** are conducted with staff members within two weeks of completing life story interviews with residents.

Research interviewers conduct post-life-story-interview assessments with staff regarding each of their assigned residents. This shorter survey examines the experience of participating in LifeBio MemoryTM's life story interview. Time 2 interviews mirror those of Time 1, except for demographic information. A series of satisfaction items related to the LifeBio MemoryTM training and experience administering the life story interview are also included in the Time 2 interview.

Final LifeBio MemoryTM materials are delivered, and a complete evaluation of the program is completed. Within 4 weeks of baseline (Time 1), final LifeBio MemoryTM materials are delivered and implemented. A Life Story Book, Snapshot Summary, and Action Plan are delivered in a digital or printed format according to the needs of the care environment. Time 3 resident and staff interviews mirror Time 1, except for demographic information, and also include satisfaction measures directly related to the use of the complete LifeBio MemoryTM product, with specific items related to use of the Life Story Book, Snapshot Summary, and Action Plan. The data collected through Time 3 staff interviews informs the commercialization plan, specifically regarding staff perceptions of the acceptability and feasibility of automated processes in the LifeBio MemoryTM app, potential reasons why residents decline participation or and/or do not complete the LifeBio MemoryTM protocol at various steps of the recruitment process, challenges and opportunities in delivering LifeBio MemoryTM, and modifications needed to sustain the program in different communities.

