## Residential Care Professionals:

During the full-scale fidelity trial, residential care professionals will be trained in the use of the revised LifeBio MemoryTM product using the associated training modules. Enrolled staff will have varying levels of prior training, background in gerontology, and/or experience working directly with older adults. Preloaded tablets with LifeBio MemoryTM will be distributed in a staggered manner for self-paced, online instruction. Each staff member is required to complete the training within one week of assignment, as well as a pre-training, baseline survey that collects demographic information, job history, previous experience with life story work, and attitudes towards person-centered care and older adults living with dementia. Other support materials, like frequently asked questions (FAQs), will also be provided for viewing. Staff members also complete a checklist and post-training survey on the tablets that gathers their opinion on 1) the length of time spent on training, 2) whether they had difficulty particular sections/content/materials, 3) whether they felt prepared to conduct life story interviews with older adults living with dementia. 4) whether they felt comfortable with the basic functionality of LifeBio MemoryTM, 5) whether they felt confident the technology would accurately convey the story of the resident living with dementia, and 6) whether they had specific questions not covered by the FAQs or training. They also have the opportunity to provide comments on their overall experience via open-ended questions.

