# **Participant Retention**

Focus Groups: As these participants from Aim 1 are planned to return for Aim 3, we maintain regular contact with focus group participants and provide updates on the project. A follow-up date for the Specific Aim 3 focus groups investigating the prototype is planned following the initial meetings, contact information is gathered, and the groups are notified at regular intervals leading in to the second round – and up to several months out, the groups are notified at one month, two weeks, and one week prior to the second round. A second round of incentives are also handed out to all participants upon completion of the second focus group (\$25 for existing LifeBio users and staff members; \$50 for stakeholders).

Clinical Trial: In order to maximize participation, research staff are very clear when talking with residents and staff that their participation will include follow-up interviews (one follow-up interview for residents approximately 1-month post baseline; two follow-ups for staff participants, within 1-month of life story interview, and 1-month after delivery of full LifeBio MemoryTM product). Because of the short time frame between data collection points, we plan for an attrition rate of approximately 10% from T1 through T3 to ensure that our recruitment and retention goals are met. To address potential attrition over the 3-month participation period, we follow sample retention strategies that have yielded low levels of attrition (approximately 10-13%) in our previous intervention programs:

- Onboarding meetings with the residential care facility sites, with project staff and site. Onboarding meetings describe the protocols and procedures of Specific Aim 3 and clinical trial.
- 2) Site liaisons identified within each site assist with the study's recruitment and LifeBio MemoryTM implementation, as well as reaching resident and staff participants to complete their research interviews.
- 3) Research staff hold bi-weekly calls with each site to provide updates on participant recruitment, program implementation, and identify areas where support is needed.
- 4) Staff compensation of \$15/interview for each timewave (Times 1-3) and site honorariums of \$500/site are processed upon completion of study requirements.
- 5) We oversampled to accommodate a reasonable level of attrition.

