Overtaxing or Overburdening Respondents with Dementia: Research interviewers are trained to use techniques and clinical procedures to avoid overtaxing or burdening respondents and to enhance communication. In past studies, we have implemented interviewing procedures specifically designed for aged and/or impaired persons. Examples include giving visual cues (choice cards), scheduling interviews at times when fatigue is less likely, and being sensitive to respondents' emotions (e.g., allowing for pauses in the interview process or taking a break so they can regain composure). Instruction in these techniques are an important part of the project's interviewer training. In addition, at the start of each interview, respondents are reminded that they are free to decline to answer any question and can end the interview whenever they choose.

Adverse Reaction: In the unlikely event that a respondent has an adverse reaction, two safeguards are in place to resolve the situation. First, the researchers involved in the study are experienced in working with this population and are prepared for coping with a respondent's emotional reactions. [name] has over 20 years of experience working directly with individuals living with dementia, as well as residential care facility staff. Second, respondents have access to the services of their referring community service agency, including experienced social workers, and are also able to receive referrals to appropriate regular communication with sites and

referring organizations to identify any problems that might arise. These procedures have been used extensively in past research.

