## Adverse Event Collection and Reporting

[name] and [name] will be informed of any serious adverse events as soon as they occur and notify the Data and Safety Monitoring Team within 24 hours of notification.

In the event of an adverse event, the following information will be reviewed:

- Participant's study status.
- How the participant was recruited into the study and the efforts that took place to retain him/her.
- The nature of the adverse event and a determination of how the participant's safety has been threatened as a result.

In most mild cases (i.e., increased stress), a recommendation will be made to discontinue the individual's participation in the intervention and/or to withdraw the participant from the study. In moderate cases (i.e., unable to cope), the participant will be referred to an identified expert (the Alzheimer's Association, a geriatric care manager, or licensed clinical social worker, etc.). If the adverse event is deemed to be very serious (i.e., suicidal risk or the health/well-being of the participant is in jeopardy), the case will be reported to the appropriate authorities to intervene on the situation immediately.

Any significant adverse events will be reported to the IRB, the NIA Program Officer, and the Safety Officer within 48 hours of knowledge of occurring. A summary of all other adverse events will be reported to the NIA Program Officer and Safety Officer quarterly, unless otherwise requested.

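### No listed post-session question and no stated staff reporting route specifically captures resident distress in the life-story interview, so an empty harms table could not be read as absence of harm

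*Combined protocol and SAP*

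**What the plan says.** The protocol's Safety Reporting section lists three risks: loss of confidentiality, overtaxing respondents with dementia, and adverse reaction. Under Adverse Event Collection and Reporting, increased stress is the example of a mild event and being unable to cope the example of a moderate one. Each tier has its own action.

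Under Specific Aim 3, "a trained staff member conducts a life story interview with a resident within a two-week period". Of these staff the Training Plan says: "Enrolled staff will have varying levels of prior training, background in gerontology, and/or experience working directly with older adults". Afterwards they are "prompted to complete a brief electronic survey on the tablet immediately after each of their assigned" interviews. On content: "The survey questions gather information on satisfaction with" four topics. The first is "interviewing the resident/quality of interaction with the resident"; the others are experience with the app, perceived advantages, and whether programme goals were met. Open note fields follow. Sessions are audiotaped where permission is given, and raters score how far staff used the trained strategies.

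Under Protection Against Risks, the overtaxing safeguard reads: "Research interviewers are trained to use techniques and clinical procedures to avoid overtaxing or burdening respondents and to enhance communication". On site contact, Participant Retention says: "Research staff hold bi-weekly calls with each site to provide updates on participant recruitment, program implementation, and identify areas where support is needed".

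For serious events, two named members of the study team are to be told at once and then "notify the Data and Safety Monitoring Team within 24 hours of notification". Significant events go to the IRB, the funder's programme officer and the Safety Officer within 48 hours of knowledge. All other events go into a quarterly summary.

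SAP section 1 includes safety in the primary objective, and SAP 8.5 plans descriptive reporting of harms.

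**The concern.** The plan foresees distress, classifies it as an adverse event and promises to report it, but describes no step that asks about it where the intervention is delivered. The survey completed straight after each session is the natural place, and its listed content is about satisfaction with the programme. Distress would enter the record only if a staff member chose to write it in a note or raise it with the researchers. Those staff are also the people delivering the programme.

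The result at stake is the harms report. If nobody is asked, an empty table has two explanations that the data cannot tell apart. The graded actions in the adverse-event section also depend on someone first recording an event, and the quarterly summary of non-serious events needs a source that the protocol does not name.

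**Working it through.** The plan gives no figure to reproduce, so the check sets the relevant sections side by side and asks of each whether it would record distress in a given session.

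- **Post-session tablet survey (Specific Aim 3).** It has the right timing and covers every session. No listed topic names distress. The nearest is quality of interaction, framed as satisfaction. Notes are open, with no stated prompt or review time.
- **Audio rating (Specific Aim 3).** It scores staff strategies from 0 to 5. No rating of the resident's reaction is listed, and recording depends on permission.
- **Time 2 staff interview (Specific Aim 3).** It repeats the Time 1 ratings of depression, anxiety, agitation and behaviour and covers the experience of the life-story interview. It comes within two weeks of the interviews according to Specific Aim 3, or within one month according to Participant Retention; the two must be reconciled. It rates the resident's general state, not an event in a session.
- **Time 3 interviews (Specific Aim 3).** They mirror Time 1 and add satisfaction items. This is the only planned follow-up interview with residents.
- **Bi-weekly calls (Screening; Participant Retention).** They cover recruitment, implementation and support needs. Adverse events are not a named item.
- **Protection Against Risks.** The interviewing techniques and the first adverse-reaction safeguard concern research interviewers and researchers. The second gives access to agency services and social workers and mentions regular contact with sites to find problems. It names no question or form.
- **Weekly review (Data and Safety Monitoring Activities).** It considers safety and risk from the programme materials, using whatever has reached the team.
- **Adverse-event section.** It covers review, action and onward reporting. It sets out no form, question or duty for facility staff.
- **SAP 4.1 to 4.3.** There are 24 outcomes, none of them a harm.

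No listed item therefore asks about distress in the session.

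**Illustration of what this costs.** Inputs: n = 107 residents analysed (SAP 3.2); planned numbers are 160 (SAP 3.1) and 242 (Specific Aim 3). Assumptions: one session per resident, independent sessions, and a capture fraction s, the share of distressed sessions that reach the record. The documents give no value for s. With zero events recorded, the one-sided 95% upper bound p on the true rate solves (1 − s·p)^n = 0.05, so p = [1 − 0.05^(1/n)] / s.

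- Every session asked about (s = 1): n = 107 gives 1 − 0.05^(1/107) = 0.0276, or 2.8%; n = 160 gives 1.9%; n = 242 gives 1.2%.
- n = 107 with s = 0.5: 0.0276/0.5 = 5.5%. With s = 0.25: 11.0%. With s = 0.1: 27.6%.

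Staff each interview 2 to 6 residents, so sessions are clustered and all these bounds are somewhat optimistic. The point is the dependence on s, which the plan gives no means of knowing.

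**The case against.** The strongest reply is that the plan does have safety routes. Enrolled staff join bi-weekly calls, site calls look for support needs, the protocol refers to contact with sites to identify problems, residents have access to social workers, and the team reviews safety weekly with an independent Safety Officer receiving reports. This stands, and it limits the point: the routes exist, but they are general, rely on someone volunteering the event, and are not tied to the session.

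Second, the protocol lists survey topics rather than item wording. The training modules and rating form are not reproduced, and the operating procedures are a separate document still in progress. A distress item or staff instruction may exist there. That also stands, so the claim is confined to what is listed.

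Third, SAP 3.2 already states the analysed sample, so a new survey item may come too late. That affects which remedy applies, not the reading of the harms table.

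A reader might also infer four stronger things that the documents do not support:

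- That the life-story session is the step most likely to cause distress. No section ranks the steps by risk.
- That no researcher is present. The protocol does not say so, and it refers to oversight of the staff.
- That mild and moderate events have no route at all. The general routes above contradict this.
- That waiting for the next call delays the start of the 24-hour clock. That clock applies to serious events, which are to be passed on at once; mild events below the significant level go to the quarterly summary. A clock that starts at awareness is not an error in itself.

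**Conclusion.** The point holds in this form: nothing listed in the plan specifically asks about resident distress in the staff-run session, and no route is stated by which facility staff report mild or moderate events to the researchers. The harms report would rest on unsolicited reports, and an empty table would be uninterpretable. The size is all sessions held, with at least one for each of the 107 analysed residents if each had an interview. The fall in information runs from a bound of about 2.8% to one that cannot be stated without knowing the capture fraction. The conclusion assumes that the instruments contain no unlisted distress item; if one exists, the remaining task is to cite it and report it. This is a change that should be made, because it is cheap and bears on a stated objective. It does not show that residents were harmed or left without support.

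**What to change.** - Add one required item to the existing post-session tablet survey: whether the resident became upset or asked to stop, with a severity grade.
- Make any adverse event since the last contact a standing question in the existing bi-weekly calls and in the protocol's Time 2 and Time 3 interviews.
- State in the adverse-event section how facility staff report events to the researchers.
- In the harms table of SAP 8.5, report the item with all completed sessions as denominator, and show the number of sessions with no answer.

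How a positive answer relates to the action tiers in the adverse-event section is for the investigators to reconcile before the item goes live.

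If sessions are already complete, review the open notes and the available recordings for distress, give the number of sessions that could be reviewed, and state in the harms report that events were collected passively.

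The cost is one survey item, one line in the call agenda and in two interview forms, and a short protocol addition. The downside is slightly longer surveys and more minor events to log and review. No treatment or endpoint changes.
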